Investigational medical product(s) [IMP], dose, and mode of administration	
IFX-1 is provided in 10 mL vials containing 100 mg IFX-1 and will be infused over a period of 30 to 60 minutes (min) via an intravenous (iv) line.
 
Placebo is provided in 10 mL vials containing sodium chloride, sodium phosphate, and Polysorbate 80. The placebo vials and content have the same appearance as the IFX-1 vials and additives.
 
Main Period (16 weeks): For each cohort, the Main Period starts at Week 0 (Day 1, immediately before first administration of IMP) and consists of a 2-week Induction Phase (ends immediately after administration of IMP at Week 2) followed by a 14-week Maintenance Phase through Week 16 (ends immediately after administration of IMP at Week 16).
 
Cohort 1 (placebo):
 
 
• Induction Phase: placebo at Weeks 0 (Days 1 and 4), 1, and 2
 
• Maintenance Phase: placebo at Week 4 and every other week through Week 16
 
 
Cohort 2 (IFX-1 400 mg q4w):
 
 
• Induction Phase: IFX-1 400 mg at Week 0 (Days 1 and 4), followed by placebo at Weeks 1 and 2
 
• Maintenance Phase: IFX-1 400 mg at Week 4, followed by alternating infusions every other week of placebo or 400 mg IFX-1 through Week 16
 
 
Cohort 3 (IFX-1 800 mg q4w):
 
 
• Induction Phase: IFX-1 800 mg at Weeks 0 (Days 1 and 4) and 1, followed by placebo at Week 2
 
• Maintenance Phase: IFX-1 800 mg at Week 4 followed by alternating infusions every other week of placebo or IFX-1 800 mg through Week 16
 
 
Cohort 4 (IFX-1 800 mg q2w):
 
 
• Induction Phase: IFX-1 800 mg at Weeks 0 (Days 1 and 4), 1, and 2
 
• Maintenance Phase: IFX-1 800 mg at Week 4 followed by IFX-1 800 mg every other week through Week 16
 

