	
Extension Period (28 weeks) – HiSCR responders
 
Subjects from all cohorts who are HiSCR responders at Week 16 will receive IFX-1 at a dose of 800 mg q4w, starting at Week 20 through Week 40. If they have a loss of response (see Definitions of Terms) during the Extension Period, they will have an optional visit 2 weeks later. Subjects who then have a loss of response at the subsequent (planned) visit will be discontinued from the study and will not switch to the non-responder schedule.
 
Extension Period (28 weeks) – HiSCR non-responders
 
Subjects from all cohorts who are HiSCR non-responders at Week 16 will receive IMP during an Induction Phase (Weeks 18 and 19), followed by IFX-1 at a dose of 800 mg q2w during the Maintenance Phase.
 
Cohort 1:
 
 
• Induction Phase: infusion of IFX-1 800 mg at Weeks 18 (Days 127 and 130) and 19
 
• Maintenance Phase: IFX-1 800 mg at Week 20 and every other week through Week 40
 
 
Cohort 2:
 
 
• Induction Phase: infusion of IFX-1 800 mg at Week 18 (Day 127), placebo at Week 18 (Day 130), and IFX-1 800 mg at Week 19
 
• Maintenance Phase: IFX-1 800 mg at Week 20 and every other week through Week 40
 
 
Cohorts 3, 4, and 5:
 
 
• Induction Phase: infusion of IFX-1 800 mg at Week 18 (Day 127), and placebo at Week 18 (Day 130) and Week 19
 
• Maintenance Phase: IFX-1 800 mg at Week 20 and every other week through Week 40
 
 
Subjects who experience Worsening or Absence of Improvement (WOAI) (see Definitions of Terms) at 2 consecutive visits during the Maintenance Period of the Extension Period will be discontinued from the study.

Study duration	
The study duration for an individual subject will be up to 48 weeks and includes the following study periods:
 
 
• Screening Period: up to 18 days before first administration of IMP (Week -4 to Week -2 [Day -28 to Day -10])
 
• Main Period: starts with the first infusion of IMP on Week 0 (Day 1) and ends at Week 16 (Day 113), after administration of IMP
 
• Extension Period: starts after administration of IMP at Week 16 and ends at Week 44
 

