#### Rationale for Dosing Regimen

The aim of treatment with IFX-1 is to reach an almost complete blockade of the overall available C5a (existing and newly produced) in human whole blood during the entire treatment period. The rate at which consumed or activated C5 can be regenerated (the so-called C5 turnover rate) is not known. It is plausible to assume that more C5 could be produced in settings of chronic inflammation than in healthy subjects, and thus more C5a could result from the ensuing activation.

From clinical studies conducted so far (IFX-1-P1.1 and -P2.1), it is known that the peak IFX-1 concentration upon administration of 4 mg/kg bw was approximately 100  $\mu$ g/mL (approximately 650 nM), which could theoretically block approximately 1200 nM of C5a. The expected half-life of IFX-1 is 3 to 4 days, thus, a biweekly dosing interval with a dose range of 400 to 800 mg in subjects with normal body weight is recommended.

In Study IFX-1-P2.3 in subjects with HS, IFX-1 administered at a weekly dose of 800 mg resulted in mean IFX-1 trough concentrations of 50.1 to 79.4 µg/mL. This dosing regimen was well tolerated, with no new safety signals, and clinical improvement of HS was demonstrated in the majority of subjects. The percentage of subjects achieving an HiSCR was higher than in the Phase III studies of adalimumab [11]. An effective dose of IFX-1 is unknown, as is the appropriate interval of administration. Therefore, 4 dosing regimens were selected for the current study to evaluate a dose-response signal for IFX-1 in subjects with HS according to the HiSCR at Week 16. All dosing regimens consist of a 2 weeks induction treatment to achieve blockade of C5a. After this induction treatment, a regular dosing schedule for maintenance treatment will start to maintain a blockade even in subjects on a low dose and in subjects in whom the entire C5 pool is enlarged and “turned over” several times. The toxicology development of IFX-1 is considered adequate to support the planned Phase II clinical study in subjects who will be treated at doses up to 1200 mg IFX-1 over a time period of 40 weeks. There were no relevant findings in the toxicology studies, which would preclude the continued clinical development of IFX-1.

Exposures and safety margins are summarized in [Table 1](#).

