For France: After each infusion of IMP administered in the Induction Phases of the Main and Extension Periods, subjects must remain at the study site for at least 60 min after end of IMP administration; appropriate treatment for potential infusion-related reactions must be available during this time.

Each administration of IMP will be recorded in detail in the source documentation and in the eCRF.

If a subject misses a visit for a scheduled infusion of IMP for any reason, the infusion must be administered as soon as possible after the scheduled time of infusion. If the scheduled infusion cannot be administered within 3 days after the scheduled time of infusion, then that infusion should be omitted and the subsequent infusion must be administered as planned.

If a subject appears at the study center for a scheduled infusion but the infusion cannot be administered due to any reason, the visit can be repeated within 3 days (if the investigator thinks that the IMP can be administered within 3 days). Otherwise, the infusion will be omitted and is documented accordingly in the eCRF.

Subjects who omit more than 2 scheduled (consecutive or non-consecutive) infusions during the Main Period will be discontinued from the study and will have a Post-Treatment FUV 3 months after discontinuation or when another HS therapy has been started (Section 6.2).

The number of unused, partially used, and empty vials will be documented and the vials will be kept until the drug accountability documentation has been checked by the monitor.

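### The single 3-day make-up rule is not reconciled with the 3- and 4-day induction gaps, so two active 800 mg infusions can fall due on the same or consecutive days

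*Combined protocol and SAP*

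**What the plan says.** Section 5.4.2 (text after Table 3) says of a missed visit that "the infusion must be administered as soon as possible after the scheduled time of infusion". If the infusion cannot be given "within 3 days after the scheduled time of infusion, then that infusion should be omitted and the subsequent infusion must be administered as planned". For a subject who attends but cannot be infused, "the visit can be repeated within 3 days (if the investigator thinks that the IMP can be administered within 3 days"). The rule makes no distinction between induction and maintenance visits.

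The induction schedules are tight. For Cohort 4 in the Main Period the Synopsis gives "Induction Phase: IFX-1 800 mg at Weeks 0 (Days 1 and 4), 1, and 2". Table 2 shows the same first three 800 mg infusions for Cohorts 3 and 5. For Cohort 1 non-responders in the Extension Period it gives "Induction Phase: infusion of IFX-1 800 mg at Weeks 18 (Days 127 and 130) and 19". The Schedules of Assessments allow ±1 day around each of these visits except Day 1.

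On dose, Section 5.4.1 lists single infusions of 400, 800 or 1200 mg. Table 1 gives exposure margins for 1200 mg, and Section 1.3 regards the toxicology programme as supporting subjects "treated at doses up to 1200 mg IFX-1 over a time period of 40 weeks". Section 5.7 says the consequences of overdose are unknown and gives no threshold. Section 5.5 keeps both induction phases double-blind.

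**The concern.** A 3-day allowance is harmless when infusions are 2 or 4 weeks apart. When they are 3 or 4 days apart, the latest permitted make-up lands on the next infusion day or the day before it. No passage moves or drops the next infusion after a make-up, so a site can follow the text and give two active infusions close together.

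This is a safety matter. The site is blinded, so it cannot tell whether the two bags are both active. For a Cohort 1 subject the pair would be the first exposure to IFX-1. The protocol also tilts towards making up a dose, because more than two omitted infusions lead to discontinuation (Sections 5.4.2 and 6.2.3).

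**Working it through.** **The plan's own figures.** Table 1 margins: 2553 / 260 = 9.8 (stated ca. 10) and 464,737 / 17,000 = 27.3 (stated ca. 27). Table 2 cumulative doses before the Week 16 infusion: Cohort 2, 5 × 400 = 2000 mg; Cohort 3, 6 × 800 = 4800 mg; Cohort 4, 10 × 800 = 8000 mg; Cohort 5, 3 × 800 + 7 × 1200 = 10,800 mg. All agree with the document.

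**Calendar check.** Latest make-up day = scheduled day + 3, compared with the next scheduled infusion in Tables 2 and 3.

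| Missed | Latest make-up | Next due | Days between | If next visit is 1 day early | Both infusions active in |
|---|---|---|---|---|---|
| Day 4 | Day 7 | Day 8 | 1 | 0 | Main Period Cohorts 3, 4, 5 |
| Day 8 | Day 11 | Day 15 | 4 | 3 | not a close pair |
| Day 127 | Day 130 | Day 130 | 0 | −1 | Extension Cohort 1 non-responders |
| Day 130 | Day 133 | Day 134 | 1 | 0 | Extension Cohort 1 non-responders |
| Day 134 | Day 137 | Day 141 | 4 | 3 | not a close pair |

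The problem does not arise in these cases:
- The Main Period Day 1 to Day 4 gap. Section 3.3 starts the Main Period at the first infusion, so a late first infusion moves Day 1.
- Cohort 2 in the Main Period. The Day 4 dose of 400 mg is followed by placebo on Day 8.
- Cohort 2 to 5 non-responders in the Extension Period. At least one infusion of each close pair is placebo.

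**Who is on these schedules.** Main Period Cohorts 3 to 5 are 3 × 35 = 105 of 175 planned subjects. At the 25% placebo response assumed in Section 10.2, about 0.75 × 35 = 26 Cohort 1 subjects would enter the non-responder induction. These are subjects on the schedule, not a forecast of events. The documents give no rate of missed infusions.

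**Amount.** Same day: 800 + 800 = 1600 mg, and 1600 / 1200 = 1.33. On consecutive days each day's amount is 800 mg, which is planned, so only the spacing is at issue.

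**Peak exposure.** Assumptions: kinetics linear in dose, and first-order decay with a half-life h of 3 to 4 days (Section 1.3). The amount just after an infusion at time t is the sum of dose × 0.5^((t − s)/h) over infusions at times s ≤ t. Concentration = amount × 260 / 1200 (Table 1). The first figure in each range is for h = 3 days and the second for h = 4.

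| Sequence | Amount (mg) | Peak (µg/mL) |
|---|---|---|
| Planned 800 mg on Days 1, 4, 8 | 1276–1438 | 277–312 |
| Planned Cohort 5, Days 1, 4, 8, then 1200 mg on Day 15 | 1453–1627 | 315–353 |
| 800 mg on Days 1, 7, 8 | 1594–1711 | 345–371 |
| 800 mg on Day 1, two on Day 7 | 1800–1883 | 390–408 |
| Two 800 mg on Day 130 (no earlier active dose) | 1600 | about 347 |

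The Extension sequence on Days 127, 133, 134 has the same spacing as Days 1, 7, 8 and gives the same values.

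Against the planned Cohort 5 peak:
- Consecutive days: 1594 / 1453 = 1.10 and 1711 / 1627 = 1.05, so 5 to 10% higher.
- Both on Day 7: 1800 / 1453 = 1.24 and 1883 / 1627 = 1.16, so 16 to 24% higher.
- Extension Day 130 pair: 1600 / 1453 = 1.10 and 1600 / 1627 = 0.98, so from 10% above to 2% below.

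**The case against.** The strongest reply is that the text is silent and does not instruct a double dose. A reader might infer from the words about giving the subsequent infusion as planned that the protocol orders both infusions. It does not: that clause governs only the case where the late infusion has been omitted. Day + 3 is an outer limit on a rule that asks for the infusion as soon as possible. A repeat visit is left to the investigator, and Section 5.4.1 refers preparation and application details to an IMP manual that is not available here and may set spacing. All of this stands. It means the passages are unreconciled rather than in direct contradiction. It does not close the gap, because Section 5.4.2 is where the late-infusion rule sits and it names no exception.

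A reader might also infer that a 1200 mg daily ceiling is breached. The documents set no daily or 24-hour limit. 1200 mg is the largest single infusion and the dose tabulated in Table 1.

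Same-day dosing is narrow. At nominal dates it needs a Cohort 1 non-responder who misses Day 127 and returns on Day 130. In the Main Period it needs the latest Day 4 make-up and the Day 8 visit taken a day early.

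There are also safeguards. Blinding hides content but not timing, so a site can see two infusions falling together. Section 5.4.2 requires at least 30 minutes of observation after each of the first two infusions in each induction phase. Section 5.7 requires close monitoring if overdose is suspected. These limit the consequences but do not tell the site what to do with the second infusion.

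**Conclusion.** The point holds as a gap in Section 5.4.2. The 3-day limit equals the first induction gap and is one day short of the second; the third gap, 7 days, is unaffected. Treatment in line with the text can bring two active 800 mg infusions together in these cases:
- On the same day: Extension Cohort 1 non-responders, with Day 127 made up on Day 130.
- On consecutive days: the same subjects on Days 133 and 134, and Main Period Cohorts 3 to 5 on Days 7 and 8. These become same-day pairs if the second visit also uses its −1 day window.

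The same-day total of 1600 mg exceeds the largest planned infusion and the dose in Table 1. A reader might infer a toxic exposure from setting a same-day peak of 390 to 408 µg/mL (margin 2553 / 408 = 6.3 to 2553 / 390 = 6.5) beside the stated margin of ca. 10. That compares an accumulated peak with a single-dose margin. On the same basis the planned Cohort 5 peak already has a margin of about 7.2 to 8.1. These figures rest on linear kinetics and one-compartment decay, which the documents do not establish.

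Nor do the documents support a claim that the dose groups in the primary analysis are distorted. The MCP-Mod dose levels are cumulative doses to Week 16, which a make-up preserves, and the Extension case comes after that endpoint.

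Frequency is unknown and probably low. The point still merits correction because a stated rule gives an unplanned result on a safety matter at blinded sites.

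**What to change.** The sponsor should reconcile the make-up rule in Section 5.4.2 with the 3- and 4-day induction spacing in Tables 2 and 3, and with the doses covered in Section 1.3, Table 1 and Section 5.4.1. Section 5.4.2 should then state how a late induction infusion and the next scheduled infusion are handled. If the IMP manual already says so, a cross-reference is enough. What the rule should be is for the sponsor's clinical team, and none is proposed here.

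The cost is a few sentences in Section 5.4.2, matching text in the IMP manual and, if wanted, a dispensing check in the IRT. The sample size and the primary analysis do not change.

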## 5.5 Randomization and Blinding

The randomization can occur at every time point between Screening and Day 1 or at Day 1 after confirmation of the Principal Investigator that the patient fulfills the eligibility criteria.

If the investigator randomizes the patient between Screening Visit and Day 1 and recognizes that the patient did not fulfill the eligibility criteria anymore at Day 1, the patient should not be treated and will be classified as early discontinuation.

For treatment during the double-blind Main Period, subjects will be centrally assigned to randomized IMP in 1 of 5 cohorts in a ratio of 1:1:1:1:1 (Section 3.1) using an Interactive Response Technology (IRT) at Day 1 stratified by Hurley Stage II and III. Complete data from the clinical HS examination must be available before randomization can occur.

The double-blind will be maintained through the Main Period and, for HiSCR non-responders, in the Induction Phase of the Extension Period.

### Emergency Identification of Investigational Medicinal Product

The IRT will be programmed with blind-breaking instructions. In case of an emergency, the investigator has the sole responsibility for determining if unblinding of a subject's treatment

---

assignment is warranted. Subject safety must always be the first consideration in making such a determination.

If the investigator decides that unblinding is warranted, he or she should make every effort to contact the sponsor before unblinding a subject's treatment assignment unless this could delay emergency treatment. If a subject's treatment assignment is unblinded, the sponsor will be notified via the IRT and the subject should discontinue treatment. The date and reason why the blind was broken must be recorded in the source documentation and in the eCRF, as applicable.

## 5.6 Procedures in Case of Specific Side Effects

To date, IFX-1 has been tested in healthy subjects and subjects with early septic organ dysfunction, complex cardiac surgery, and HS. An overview of side effects (i.e., ADRs that occurred in these studies) is provided in the Investigator's Brochure.

If a side effect occurs or is suspected after administration of IMP, subjects must be closely monitored and carefully observed, and as applicable the side effect must be reported as an AE (Section 9). Any treatment deemed as medically appropriate should be initiated.

In case of the following specific types of side effects, the procedures reported below must be applied.

**Infections:** because IFX-1 blocks C5a, there is a theoretical risk of an increased rate of infections. Therefore, the investigator (and other health care professionals who take care of the subjects) should be alert to signs and symptoms of infections in general. In case a subject develops a clinical picture that is difficult to distinguish from that associated with invasive infection, routine blood cultures and early start of antibiotic treatment is recommended. In subjects with bacterial infection, depending on the severity of the infections, it is important that concomitant antibiotic therapy be administered during treatment with IFX-1 to ensure appropriate control of the source of the infection. The investigator should pay close attention to the choice of an appropriate broad spectrum antibiotic treatment according to applicable guidelines. The IMP can be temporarily or permanently interrupted at the investigator's discretion. Any invasive infection has to be reported as an adverse event of special interest (AESI) (Section 9.3).

**Meningitis/Meningococcal Sepsis:** in case of signs of meningitis at any time during the study period, the subject must be carefully observed and the guideline for "ambulatory acquired bacterial meningoenzephalitis"[22] should be followed. This includes lumbar puncture, blood culture testing, immediate start of treatment with dexamethasone and iv antibiotics (combination therapy with ampicillin and 3rd generation cephalosporin), and search for infectious focus (e.g., computed tomography or magnetic resonance tomography). The IMP should be interrupted immediately in case of signs and symptoms of meningitis and withdrawn if meningitis is confirmed.

**Infusion-Related Reactions/Anaphylactic Reactions and Acute Systemic Allergic Hypersensitivity:** In case of any severe, acute systemic hypersensitivity reaction during, or shortly after, infusion of IFX-1, the infusion should be stopped immediately and the subject discontinued from further dosing. In such cases, subjects should be closely monitored for any changes in blood pressure, heart rate, metabolic conditions, or organ function, and appropriate measures should be taken to stabilize all vital signs. Fluid resuscitation may be needed, as well as vasopressor therapy or other measures to treat changes in blood pressure, vital signs, or metabolic conditions in general. In cases of emergency with immediate life-threatening potential such as cardiac arrest or similar life-threatening changes, appropriate cardio-pulmonary resuscitation should be started immediately according to applicable guidelines, or as established at the study sites through existing standard operating procedures or other algorithms for cardio-pulmonary resuscitation according to current recommended resuscitation guidelines.

---

For any potential infusion-related event, the physician should check for a potentially developing or existing anaphylactic reaction. In case an anaphylactic reaction is anticipated, appropriate immediate actions should be taken according to the severity or stage of the detected anaphylactic reaction as recommended by existing guidelines for the treatment of anaphylactic reactions or, if established at the study sites, according to available standard operating procedures or algorithms.

If the investigator abstains from further dosing, the subject should be discontinued from the study and handled as drop-out.

In case of an emergency or other situation in which it is medically imperative for the investigator to identify the IMP that a subject has received or is receiving during the Main Period and during the Induction Phase of the Extension Period, the procedure for emergency identification of IMP described in Section 5.5 must be followed.

## 5.7 Overdose

The consequences of an overdose with IFX-1 are not known.

If overdosing occurs or is suspected, subjects must be closely monitored and carefully observed for any symptoms. In case of any symptoms, treatment as deemed medically appropriate by the investigator should be initiated. Overdoses must be recorded as treatment-emergent adverse events (TEAEs).

## 5.8 Prior and Concomitant Therapy

Any medication, vaccine (including, but not limited to, over-the-counter or prescription medicines such as aspirin, antacids, vitamins, mineral supplements, and/or herbal supplements), or procedure (e.g., phototherapy or laser-surgical therapy) that the subject received during 3 months before Screening, at Screening, or receives during the study, must be recorded in the source documentation and in the eCRF, with details on the reason for use, date(s) of administration (with start and end dates), and dosing information, including dose, route, and frequency of administration.

